□ 7) Research on individual or group characteristics or behavior (including, but not limited to, research on perception, cognition, motivation, identity, language, communication, cultural beliefs or practices, and social behavior) or research employing survey, interview, oral history, focus group, program evaluation, human factors evaluation, or quality assurance methodologies. (Note: Some research in this category may be exempt from the HHS regulations for the protection of human subjects. This listing refers only to research that is not exempt.)

MODIFICATION REQUEST SECTION

0 unresolved
comment(s)

*** If this modification changes the scope of your activities to include COVID-19 related research, please insert "COVID19" at the start of your Project and Short Titles.***

Select One:

- This modification does not increase risk to study participants.
- This modification may or will increase risk to study participants.

Is this modification request due to an Unanticipated Problem/Adverse Event, or Protocol Violation?

- Yes
- No

In your professional opinion, does this modification involve information that might relate to a subject's willingness to continue to take part in the research?

- Yes
- No

If yes, state how the information will be communicated to subjects (i.e., re-consent, send letter, etc.):

For each proposed modification, include a justification.

Example: [name], is being added as co-investigator because she has expertise with the subjects on this protocol. She has completed human subject protections training, and is authorized to obtain consent.

[name] , [name] and [name] are being added as project assistance for data analysis because they have expertise with the subjects on this protocol.

PROJECT INFORMATION**0 unresolved comment(s)**

Title of Project: (Use the exact title listed in the grant/contract application, if applicable).

If your research investigates any aspect of COVID-19, please include "COVID19" at the beginning of your Project Title and Short Title

Role of aspirin in maternal endothelial dysfunction and uterine artery blood flow in women at risk for preeclampsia

Short Title Description

Please use a few key words to easily identify your study - this text will be displayed in the Dashboard listing for your study.

ASPERIN Trial

Anticipated Ending Date of Research Project: 3/31/2026

Maximum number of human subjects (or records/specimens to be reviewed) 209

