The study population will include pregnant women between the ages 18 and 45 years enrolled as cases and controls. Women at high risk for preeclampsia will be enrolled as cases and those without risk factors for preeclampsia will be approached to serve as a control population. Approximately 250 eligible women will be enrolled in this study (50 in the normal control arm, 100 in the low dose 81 mg per day arm, and 100 in the 162 mg per day arm). Eligible patients will be recruited from UK clinics and the UK Good Samaritan ultrasound unit at the time of their scheduled prenatal visits or ultrasound appointments. Women who plan to deliver at University of Kentucky Chandler Hospital will be approached for enrollment.

The risk factor assessment to screen women at high risk for preeclampsia include:

1. History of preterm preeclampsia, especially when accompanied by an adverse outcome
2. Chronic hypertension
3. Type 1 and Type 2 diabetes
4. Renal diseases
5. Autoimmune disease

Exclusion criteria include:

1. Pregnant women younger than 18 years or older than 45 years
2. Multiple gestations
3. History of allergy (urticaria or anaphylaxis) to aspirin or aspirin related products asthma that worsens after aspirin use
4. Patients with gastrointestinal or genitourinary bleeding
5. Patients with peptic ulcer disease
6. Patients with severe liver dysfunction
7. Patients who have undergone bypass surgery
8. Patients on anticoagulant medication(s)
9. Women with anomalous fetus

Recruitment and data collection is expected to last throughout 2018-2022 academic years. Data analysis is expected to be accomplished during 2019-2022 academic years.

Attachments

Indicate the targeted/planned enrollment of the following members of minority groups and their subpopulations. Possible demographic sources: [Census Regional Analyst Edition](#), [Kentucky Race/Ethnic Table](#), [Kentucky Population Data](#).

(Please note: The IRB will expect this information to be reported at Continuation Review time for Pre-2019 FDA-regulated Expedited review and Full review applications):

Participant Demographics

	Cisgender Man 	Cisgender Woman 	TGNB/TGE 	Unknown/Not Reported
American Indian/Alaskan Native:	0	2		
Asian:	0	10		
Black/African American:	0	35		
Latinx:	0	25		
Native Hawaiian/Pacific Islander:	0	2		
White:	0	166		
American Arab/Middle Eastern/North African:		1		
Indigenous People Around		1		

the World: _____

More than One Race:	8		
Unknown or Not Reported:	0	0	

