List your research objectives. Please include a summary of intended research objectives in the box below.

The objective of our study is to determine if low dose aspirin has a dose dependent response to modify maternal endothelial dysfunction and impedance in uterine arteries when used in the prophylaxis of preeclampsia prevention in women identified as at high risk for development of preeclampsia.

Another objective of our current study is to understand the important mechanism of prevention of pre-eclampsia with the ultimate goal to improve targeting of therapy to pregnant women who will benefit from aspirin exposure in pregnancy. We will accomplish this by evaluating ATL/LXA4 concentrations as a mechanism of aspirin benefit.

Study Design

Describe and explain the study design (e.g., observational, secondary analysis, single/double blind, parallel, crossover, deception, etc.).

- **Clinical Research:** Indicate whether subjects will be randomized and whether subjects will receive any placebo.
- **Community-Based Participatory Research:** If you are conducting [community-based participatory research \(CBPR\)](#), describe strategies for involvement of community members in the design and implementation of the study, and dissemination of results from the study.
- **Qualitative research:** Indicate ranges where flexibility is needed, if a fixed interview transcript is not available, describe interview topics including the most sensitive potential questions.
- **Research Repositories:** If the purpose of this submission is to establish a Research Repository (bank, registry) and the material you plan to collect is already available from a commercial supplier, clinical lab, or established IRB approved research repository, provide scientific justification for establishing an additional repository collecting duplicate material. Describe the repository design and operating procedures. For relevant information to include, see the [UK Research Biospecimen Bank Guidance](#) or the [UK Research Registry Guidance](#).

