This is a single center, prospective, randomized, open-label clinical trial. The experimental group will include pregnant women who are identified at high risk for preeclampsia either by history, presence of risk factors, or abnormal uterine artery Doppler impedance. They will be divided into two groups based on their body mass index (BMI) (<30 and =30). Patients in each group will be randomized to receive either aspirin 81 mg (1 tablet of baby aspirin) or aspirin 162 mg (2 tablets of baby aspirin) daily initiated between 11 and 16 weeks of gestation and continued until 36 weeks of gestation. There will be a third control group of pregnant women at low risk for preeclampsia based on their risk factor assessment to provide baseline data. The control group will not receive aspirin. Both of the experimental and control groups will be assessed with uterine artery Doppler studies and FMD of the brachial artery at three different time points in pregnancy: at enrollment between 11 and 16 weeks, between 18 and 22 weeks (+/- 7 days), and between 28 and 32 weeks of gestation(+/- 7 days). We will obtain baseline blood and urine samples at the time of enrollment and later between 28 and 32 weeks (+/- 7 days) to assess salicylate levels, thromboxane and endothelin-1 levels. We will also obtain cord blood and placental samples from the experimental and control population at the time of delivery.

Attachments

Subject Recruitment Methods & Advertising

Describe how the study team will identify and recruit subjects. Please consider the following items and provide additional information as needed so that the IRB can follow each step of the recruitment process.

- How will the study team identify potential participants?
- Who will first contact the potential subjects, and how?
- Will you use advertisements? If so, how will you distribute those?
- How and where will the research team meet with potential participants?
- If applicable, describe proposed outreach programs for recruiting women, minorities, or disparate populations.
- How you will minimize undue influence in recruitment?
- Attach copies of all recruiting and advertising materials (emails, verbal scripts, flyers, posts, messages, etc.).

For additional information on recruiting and advertising:

- [IRB Application Instructions - Advertisements](#)
- [PI Guide to Identification and Recruitment of Human Subjects for Research](#)

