The research procedures including patient enrollment will happen at the time of their routine prenatal visits and no additional visits for the purpose of this research are anticipated. The procedures patients will undergo during their visits and the timeline are shown in the attached table. The experimental group will include pregnant women who are identified at high risk for preeclampsia either by history, presence of risk factors, or abnormal uterine artery Doppler impedance. They will be divided into two groups based on their body mass index (BMI) (<30 and >=30). Patients in each group will be randomized to receive either aspirin 81 mg (1 tablet of baby aspirin) or aspirin 162 mg (2 tablets of baby aspirin) daily initiated between 11 and 16 weeks of gestation and continued until 36 weeks of gestation. There will be a third control group of pregnant women at low risk for preeclampsia based on their risk factor assessment to provide baseline data. The control group will not receive any aspirin.

After their initial enrollment, patients in the experimental group will be divided into 2 groups based on their body mass index (BMI) : <30 and >=30. Patients in each group will be randomized to receive aspirin 81 mg(1 low-dose aspirin tablet) or aspirin 162 mg (2 low dose aspirin tablets per day) daily until 36 weeks of gestation. Prescribing low dose aspirin is part of the standard prenatal care for women who are identified as at high risk for preeclampsia.

The prescription for aspirin for the patients enrolled in the study will be sent to the UK Good Samaritan Hospital outpatient pharmacy. When patients are randomized to Aspirin 162 mg (2 tablets of baby aspirin) and there is an additional cost to the patient due to the higher dose. The Division of Maternal Fetal Medicine at UK will receive a monthly statement from UK Good Samaritan Hospital pharmacy for every dose of 162mg that was filled during the previous month.

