Patients in both the experimental and control groups will undergo two sets of ultrasound assessments - uterine and brachial arteries, during their routine prenatal ultrasound evaluation at different time points in their pregnancy at UK Good Samaritan hospital. Initial assessment would be during their initial enrollment less than 16 weeks of gestation. The other two would be between 20 and 22 weeks (+/- 7 days) and between 28 and 32 (+/- 7 days) weeks during their routine ultrasound evaluation for fetal anatomy and fetal growth respectively. During their ultrasound visit, after completion of their routine evaluation indicated for that visit, doppler assessment of the uterine arteries will be done. Following this, Doppler assessment of the brachial artery will be performed known as the flow mediated dilation (FMD).

The baseline diameter of the brachial artery will be first recorded using the ultrasound transducer probe. Thereafter a blood pressure cuff will be placed around the forearm distal to the ultrasound probe and inflated to 25-50 mm Hg above the systolic arterial pressure for 5 minutes to elicit a reactive hyperemic stimulus. The cuff will then be deflated and the longitudinal image of the brachial artery will be obtained continuously from 30 seconds before and 2 minutes after the cuff deflation. Flow mediated dilation will be calculated using the following equation: FMD (%) = (Peak diameter - Baseline diameter) / Baseline diameter

Patients will also provide an extra tube of blood and urine specimen collected during their routine prenatal laboratory evaluation performed at the time of first trimester screening and for gestational diabetes screening in the late second/early third trimester. Finally, cord blood and will be collected in 15 patients from each group to assess whether the variation in dose results in appreciably greater fetal cord blood concentrations. The first 15 deliveries from each group in the study will be selected for cord blood and placental collection at the time of delivery. Medical records will be abstracted to collect demographic information, medical and prenatal history, treatment course, ultrasound information, information related to delivery and neonate after birth (Birth weight, gender, APGARS and neonatal complications).

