Inserted	1031173	104560	10446600	SP	N	[name]	[contact]						N	Data Analysis/Processing		P	N	ash231	4/28/2025 10:06:22 AM	N			

Modification Comment by [name] - ORI to PI on 4/28/2025 10:13:11 AM
Please add the changes being made to "[name]" - highlighted in study personnel section but not included here.

Statistical Analysis Plan NCT03893630 6/27/2025

To begin, continuous variables (age, BMI, gestational age at delivery, etc.) will be summarized with descriptive statistics (n, mean, standard error); categorical variables (e.g., pre-eclampsia, method of conception, etc.) will be summarized with counts and percentages.

The primary outcome, difference in uterine artery pulsatility index (PI) will be calculated as the difference in PI for each patient between each trimester visit. PI at each visit will be calculated by averaging left-side and right-side PIs from each of three (or all available) images on each side for each patient using ultrasound technology. For a very limited number of images identified using clinical expertise, the MATLAB code below will be used to produce PI values if ultrasound technology is insufficient.

An independent and automated image analysis pipeline will be developed using R to crop images and MATLAB to perform image analysis. For each available ultrasound image, an estimated mean PI will be calculated as the average of the PI from each analyzable waveform. For each patient at each visit, left- and right-side estimates will be obtained using the median of the available image-level estimates, since the median is more robust to outliers resulting from images that might be difficult to read. Finally, the mean PI for each patient at each visit will be calculated using the average of the left- and right-side estimates. Means and SDs of these indices will be compared to (1) ensure that there are no drastic differences from the values calculated using the ultrasound technology and the alternative pipeline, and (2) demonstrate the robustness of the calculated primary outcome values.

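### The SAP names no adjustment for enrolment PI or BMI stratum; for changes from enrolment, adding both to the 162 versus 81 mg comparison should gain precision at no data cost

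*Combined protocol and SAP*

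**What the plan says.** The Objectives section sets out "to determine if low dose aspirin has a dose dependent response", so the randomised 162 versus 81 mg contrast carries the main inference. The Study Design section splits high-risk women by BMI (<30, ≥30) and then states: "Patients in each group will be randomized to receive either aspirin 81 mg" or 162 mg.

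Uterine artery PI is scanned at enrolment and at two later windows. Research Procedures puts the first scan at entry ("Initial assessment would be during their initial enrollment less than 16 weeks of gestation") and the BMI split, followed by randomisation, after it: "After their initial enrollment, patients in the experimental group will be divided into 2 groups based on their body mass index (BMI").

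The SAP (dated 6/27/2025) gives the primary outcome as "difference in uterine artery pulsatility index (PI) will be calculated as the difference in PI for each patient between each trimester visit". The rest of its available text covers descriptive summaries and how PI is read from images. BMI appears only among the variables to be summarised. No test, model, covariate or stratification term is given for comparing the arms.

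On size, the Subject Demographics section plans "100 in the low dose 81 mg per day arm, and 100 in the 162 mg per day arm", with 50 controls. The Project Information section states "Maximum number of human subjects (or records/specimens to be reviewed) 209".

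**The concern.** With a change score as the outcome and no model named, the natural default is to compare mean changes between the two dose arms. That fixes the coefficient on enrolment PI at 1. If the true slope of follow-up PI on enrolment PI is below 1, the change score over-corrects: an arm that starts higher by chance tends to show the larger fall, and this adds noise to the dose estimate. Regression on enrolment PI estimates the slope instead of imposing it.

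BMI group is a factor in the randomisation. If it predicts PI, leaving it out of the model makes the standard error larger than it need be.

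At stake is the precision of the dose comparison in a single-centre trial whose application caps enrolment at 209 against about 250 in the population description. Naming the model in advance also removes a choice between raw and adjusted results, which is useful in an open-label trial.

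**Working it through.** **Plan figure to reproduce.** None. The documents give no sample-size calculation, alpha, power, PI SD or correlation.

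**Inputs from the documents.** 100 women per dose arm (Subject Demographics); cap of 209 in total (Project Information); dose randomised within two BMI groups (Study Design); PI at enrolment and two follow-up visits.

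**Assumptions.** Correlation r between enrolment and follow-up PI of 0.3–0.7; ratio L of follow-up SD to enrolment SD of 1, then 0.7–1.2; two-sided 5% test, 80% power.

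**Variance per woman, in units of the enrolment variance**

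- Change from enrolment: 1 + L² − 2rL = L²(1 − r²) + (1 − rL)²
- Adjusted for enrolment PI: L²(1 − r²)

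The adjusted variance is never the larger. The two are equal only when the slope rL is 1. The extra term (1 − rL)² is the chance enrolment imbalance that the change score carries, so noise and imbalance are one loss, not two.

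**Equal SDs (L = 1).** The ratio becomes (1 − r²)/[2(1 − r)] = (1 + r)/2.

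| r | Change, 2(1 − r) | Adjusted, 1 − r² | Ratio | Equivalent n per arm, 100/ratio |
|---|---|---|---|---|
| 0.3 | 1.40 | 0.91 | 0.65 | 154 |
| 0.5 | 1.00 | 0.75 | 0.75 | 133 |
| 0.7 | 0.60 | 0.51 | 0.85 | 118 |

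A simulation with 100 per arm, fitting dose, enrolment PI and a BMI group with no effect, gave 67%, 77% and 87%. The extra parameters cost little.

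**Detectable difference**, 2.80 × √(2 × variance/n), in enrolment SDs:

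| n per arm | r | Change | Adjusted |
|---|---|---|---|
| 100 | 0.3 | 0.469 | 0.378 |
| 100 | 0.7 | 0.307 | 0.283 |
| 84 | 0.3 | 0.511 | 0.412 |
| 84 | 0.7 | 0.335 | 0.309 |

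The 84 is 209 × 0.4 = 83.6, assuming the planned 100:100:50 split is kept. With 100 per arm, a difference that has 80% power with the raw change has 93.5%, 90% and 86% with adjustment at r = 0.3, 0.5 and 0.7.

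**Unequal SDs**, ratio L²(1 − r²)/(1 + L² − 2rL):

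| L | r = 0.3 | r = 0.5 | r = 0.7 |
|---|---|---|---|
| 0.7 | 0.417 | 0.465 | 0.490 |
| 0.85 | 0.542 | 0.621 | 0.692 |
| 1.2 | 0.762 | 0.871 | 0.966 |

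The range widens to 42–97%.

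**Visit 2 to visit 3 difference, adjusted for enrolment PI.** With equal SDs and equal correlations between all visits, enrolment PI is uncorrelated with this difference, so the ratio is 1.00. If correlation decays as r, r² (AR(1)), the ratio is 1 − r²(1 − r)/2 = 0.968, 0.938 and 0.926. The gain is 0–7%.

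**Follow-up PI or change as the response.** Change is follow-up minus enrolment PI. Once enrolment PI is in the model, switching between the two responses only moves its coefficient by 1. The dose estimate and standard error are identical.

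**The case against.** The strongest reply is that the quoted sentence only defines a variable. It does not prescribe an unadjusted test, and an outcome expressed as a change is fully compatible with adjustment. This stands. A reader might infer that the SAP commits to a raw two-arm comparison of changes. It does not; that is the implied default when no model is given. The available SAP text may also be incomplete, since it points to code further down that does not follow.

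The size also depends on unstated quantities. At r = 0.7 and L = 1.2 the ratio is 0.966, almost no gain. This stands too, and is why 65–85% cannot be quoted without the equal-SD condition, or applied to the visit 2 to 3 difference that the definition also covers.

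Third, that enrolment PI precedes allocation is inferred from the order of events in Research Procedures. No section fixes the sequence of scan, allocation and first tablet. The inference is reasonable but should be made explicit.

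A reader might also infer that the dose estimate is biased, particularly because Study Design admits women "identified at high risk for preeclampsia either by history, presence of risk factors, or abnormal uterine artery Doppler impedance", a route absent from the Subject Demographics risk list. The documents do not support this. Both dose arms pass through the same entry rule before randomisation, and a raw change score is unbiased over repeated randomisations. Selection on enrolment Doppler could affect within-arm changes or comparisons with the non-randomised controls, but by an amount the documents do not determine.

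**Conclusion.** The point holds as a free improvement in precision for the randomised dose contrast. For changes from enrolment (visit 1 to 2 and visit 1 to 3), adjustment for enrolment PI cannot increase large-sample variance, whatever the correlation. Its size is conditional: 65–85% of the unadjusted variance with correlation 0.3–0.7 and equal SDs, 42–97% with an SD ratio of 0.7–1.2. For the visit 2 to 3 difference it is little or nothing. A BMI-stratum gain would come on top, but the documents give no basis for a figure. Nothing here shows bias, an error in the outcome definition, or a wrong test in the SAP.

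**What to change.** Add a paragraph to the SAP:

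- Estimate the 162 versus 81 mg effect by regressing PI at each follow-up visit, or the change from enrolment, on dose, enrolment PI and BMI stratum (<30, ≥30).
- Define enrolment PI as the scan taken before allocation. Do not adjust the dose effect for second-visit PI, which is measured after randomisation.
- Leave the outcome definition as written. Report the visit 2 to 3 difference separately, or from the same longitudinal model, so that it is not dropped.

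The cost is the drafting and two degrees of freedom, with no new data, visits or patients. This should be settled before the dose comparison is run. If it has already been run, report adjusted and unadjusted results together and state which was specified first.

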Women will be screened for any history of allergy to aspirin or aspirin related products, history of gastrointestinal or genitourinary bleeding, history of gastric bypass surgery, peptic ulcer disease or liver dysfunction prior to initiating aspirin to minimize undesirable side effects of aspirin. Patients on anticoagulant medication(s) will be excluded from this study. A data and safety monitoring plan will be implemented.

They can choose to leave the study at any time without any consequences to the standard prenatal care they would receive. Risk of breech of confidentiality - Patients' data will be de-identified and will be assigned a coded identification number. Women will be informed that their data will be stored in a locked cabinet behind a locked door or on a password protected computer behind a locked door in the PI's office located in the [name]. All possible safety measures will be initiated to protect patient information. Despite all this, should any breech occur, we will contact patients immediately and work with IRB to correct any problems

[UK IRB policies](#) state that IRB-related research records must be retained for a minimum of 6 years after study closure.
Check this item to confirm that you will retain all IRB-related records for a minimum of 6 years after study closure.

Payment

Describe the incentives (monetary or other) being offered to subjects for their participation. If monetary compensation is offered,

indicate the amount and describe the terms and schedule of payment. Please review [this guidance](#) for more information on payments to subjects, including restrictions and expectations.

The subjects will not be offered any incentives for their time during participation in the research study

Costs to Subjects

Include a list of services and/or tests that will not be paid for by the sponsor and/or the study (e.g., MRI, HIV). Keep in mind that a subject will not know what is "standard" – and thus not covered by the sponsor/study – unless you tell them.

Patients' insurance company, Medicare, or Medicaid will be responsible for the costs of all care and treatment that they would normally receive for any conditions they may have. These are costs that are considered medically necessary and will be part of the care they receive even if they do not take part in this study.

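### PI differences that need the 28–32 week scan are undefined for women who deliver or leave before it, and the SAP has no rule for a missing visit

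*Combined protocol and SAP*

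**What the plan says.** The primary-outcome paragraph of the SAP states that the outcome will be calculated as the "difference in PI for each patient between each trimester visit". There are three visits, so up to three differences exist per woman: first to second, second to third, and first to third. None is named as primary.

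Within a visit, PI is obtained by "averaging left-side and right-side PIs from each of three (or all available) images on each side for each patient". This deals with missing images. Nothing in the SAP deals with a missing visit.

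The protocol's Study Design section places the scans "at enrollment between 11 and 16 weeks, between 18 and 22 weeks (+/- 7 days), and between 28 and 32 weeks of gestation(+/- 7 days". Research Procedures says "The other two would be between 20 and 22 weeks (+/- 7 days) and between 28 and 32 (+/- 7 days) weeks". The two sections agree on the third window but not on the second, and should be reconciled.

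On withdrawal, the section on records, privacy and confidentiality says of participants: "They can choose to leave the study at any time without any consequences".

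The study-population text plans "50 in the normal control arm, 100 in the low dose 81 mg per day arm, and 100 in the 162 mg per day arm". Only the two aspirin arms are randomised. Project Information gives a maximum of 209 subjects, which does not match 250; that is a separate discrepancy.

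Neither document gives an analysis set, a between-arm model, a rule for delivery or pregnancy loss before the third scan, or an expected loss rate.

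**The concern.** When no rule is written, the definition of the outcome decides who is counted. For the two differences that involve the third visit, only women scanned at 28–32 weeks have a value. A woman with enrolment and second-visit scans contributes nothing to those comparisons, although she has two PI measurements.

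The loss need not be random. The background text calls mean PI the most predictive Doppler index for preeclampsia, and the trial enrols women at high risk of that disease. Preeclampsia can end a pregnancy before the third scan. The risks-and-benefits section allows that the 162 mg group may see a larger reduction in preeclampsia. If so, the women missing at the third visit could differ between arms in number and in PI.

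Two things are at stake: precision, which is lost whatever the cause of missingness, and possible bias, whose size and sign must be worked out rather than assumed.

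**Working it through.** The plan states no effect size, SD, power or loss rate, so there is no planned figure to reproduce. Everything below rests on labelled assumptions.

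**Inputs.** From the documents: 100 women per aspirin arm and three visits. Assumed: PI has SD 1 at each visit; correlations are 0.5 (visits 1–2), 0.6 (2–3) and 0.4 (1–3); 8% of women are lost at random before visit 3; a fraction p has severe early disease; 81 mg loses all of these before visit 3 and 162 mg loses half; neither dose changes PI itself.

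**1. Who has a value.** Scans at visits 1 and 2 only: the 1-to-2 difference exists; 1-to-3 and 2-to-3 do not. Scans at 1 and 3 only: just 1-to-3 exists. Enrolment scan only: none exists.

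**2. Precision of the 1-to-3 contrast at p = 8%.** Expected completers are 100 × 0.92 × 0.92 = 84.6 (81 mg) and 100 × 0.92 × 0.96 = 88.3 (162 mg), and √(1/84.6 + 1/88.3) = 0.152.
- Raw change: SD √(2(1 − 0.4)) = √1.2 = 1.095; SE = 1.095 × 0.152 = 0.167.
- Adjusted for enrolment PI: SD √(1 − 0.4²) = √0.84 = 0.917; SE = 0.917 × 0.152 = 0.139.

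Simulation gave 0.167–0.168 for raw change and 0.140–0.144 for a longitudinal model on all visits, so nearly all the gain comes from enrolment PI. The SE ratio is √((1 + ρ)/2), where ρ is the 1–3 correlation: 0.775, 0.837, 0.894 and 0.949 for ρ = 0.2, 0.4, 0.6 and 0.8.

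**3. Bias of the raw change.** Let g be the growth in the severe cases' PI excess from visit 1 to visit 3. Completers on 81 mg include no severe cases. Those on 162 mg include a fraction (p/2)/(1 − p/2). Hence bias = g × (p/2)/(1 − p/2), where a positive value makes 162 mg look worse.

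| p | (p/2)/(1 − p/2) | excess 1, 1.5, 2 (g = 1) | constant (g = 0) | excess 2, 1.5, 1 (g = −1) |
|---|---|---|---|---|
| 4% | 0.02/0.98 | +0.020 | 0 | −0.020 |
| 8% | 0.04/0.96 | +0.042 | 0 | −0.042 |
| 12% | 0.06/0.94 | +0.064 | 0 | −0.064 |

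Simulation agreed within Monte Carlo error. At p = 1% and 2% with g = 1 the formula gives 0.005/0.995 = 0.005 and 0.01/0.99 = 0.010. At p = 8% the bias is a quarter of one SE (0.042/0.167).

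**4. Whether a longitudinal model removes it.** Such a model in effect predicts the missing visit-3 value from visits 1 and 2. Under the assumed correlations the weights are (0.4 − 0.5 × 0.6)/0.75 = 0.133 and (0.6 − 0.5 × 0.4)/0.75 = 0.533. The remaining bias is about (p/2) × (true minus predicted visit-3 excess). At p = 8%:
- Rising: predicted 0.133 × 1 + 0.533 × 1.5 = 0.933; bias 0.04 × (2 − 0.933) = +0.043.
- Constant at 1: predicted 0.667; bias 0.04 × 0.333 = +0.013.
- Falling: predicted 0.133 × 2 + 0.533 × 1.5 = 1.067; bias 0.04 × (−0.067) = −0.003.

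The model leaves the rising-excess bias in place, adds a small one where the raw change has none, and nearly removes the falling-excess one. It is not a cure for informative loss.

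**5. Worst-rank analysis.** With p = 4, 8 and 12% the simulated probability index was 0.506, 0.514 and 0.520 in favour of 162 mg. Its null SE is √(201/(12 × 100 × 100)) = 0.041, so it would rarely detect a difference of this size.

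**The case against.** The strongest reply is that the paragraph only defines a variable. A reader might infer that the SAP prescribes a complete-case analysis, or that women who leave early drop out of the primary outcome altogether. Neither is supported: no between-arm analysis is described, and a woman scanned twice keeps her first-to-second difference. This stands. The defect is a missing rule, not a stated exclusion.

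A reader might also infer that the bias runs against whichever dose works better. That holds only if the severe cases' PI excess grows between visits. A woman whose PI is equally high throughout does not shift a change score. The documents give no trajectory and no rate of delivery, loss or withdrawal before the third scan. This also stands, and it rules out any unconditional claim about direction or size.

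Third, the proposed model does not cure informative loss, and the worst-rank result is partly built in: the scenario gives one arm fewer early deliveries and then ranks those as worst. It also mixes a clinical outcome into a mechanistic measure of impedance. This limits the worst-rank analysis to a sensitivity role.

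Finally, the trial is open-label, recruitment was expected in the 2018–2022 academic years, and the SAP is dated 6/27/2025, so a model chosen now could look post hoc. That is a reason to document when it was fixed. It does not justify leaving the rule unwritten, since any rule chosen later would be more exposed to the same criticism.

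**Conclusion.** The point holds in a limited form. Differences that need the 28–32 week scan are undefined for women without it, and the SAP says neither how those women are handled nor which visit pair is primary. Analysing raw differences would set aside partly observed women and give up precision: an SE of about 0.17 against 0.14 SD with 100 per arm and an assumed 1–3 correlation of 0.4, with a smaller gain if the correlation is higher.

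Informative loss is plausible, but its effect cannot be sized or signed from the documents. Over assumed early loss of 4–12%, halved by one dose, it ranges from about 0.065 SD against the better arm, through zero, to a similar amount in its favour. These amounts are small beside the SE. The case for change therefore rests on the missing rule and on precision, not on a demonstrated bias.

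**What to change.** Amend the SAP before arm-level results are examined:

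1. Analyse all observed visit-level PI values of all randomised women in one longitudinal model, with arm-by-visit terms and enrolment PI in the model. Name the visit contrast that is primary. This keeps women with one follow-up scan. State that it does not by itself remove bias from informative loss.
2. Tabulate missing visits by arm and by reason: delivery for preeclampsia, other delivery, pregnancy loss, withdrawal, or scan not done.
3. As a sensitivity analysis only, rank women who delivered for preeclampsia or lost the pregnancy before the third scan as worst, and note that this mixes a clinical outcome into the PI measure.

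No new data collection should be needed: delivery information is already abstracted from records, and the SAP already summarises gestational age at delivery and preeclampsia. The cost is modest programming, one additional sensitivity result, and a dated record that the model was fixed before arm-level results were seen. The documents do not say whether such results have already been viewed; if they have, the amendment should say so.
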